- 4) After approximately 6 months from study enrollment and, if necessary, adjusted within a limit of 30 days to have this assessment done prior to treatment with either allogeneic HCT or additional non-transplant therapies.

Protocol 2368.00

- 5) At 3, 6, 12, and 18 months after day 0 of allogeneic HCT for recipients of HTC or at 9, 12, 18, and 24 months from study enrollment for patient not treated with HCT.

8.1.16 **Satisfaction Surveys:**

The patient will complete two satisfaction surveys: Damian's Satisfaction with Medical Care Scale and Holmes-Rovner's Satisfaction with Treatment Scale[101].

Satisfaction with doctor-patient communication will be assessed with a satisfaction scale published by Damian. Seven items measured on 5 point Likert scale ("completely dissatisfied" to "completely satisfied") and summed to give a total satisfaction score (range 5-35). For example, items include satisfaction with doctor's explanation of the patient's condition, amount of information provided, opportunity to ask questions, honesty, and willingness to discuss patients' fears. This scale detected differences in satisfaction between patients who were or were not provided summary letters of their consultations (32.5 vs. 30, $p = 0.01$).

The Holmes-Rovner's 6 item Satisfaction with Decision Scale will be used to measure satisfaction with treatment choice. The scale is written at an 8th grade level and takes approximately 1 minute to complete. It focuses more on actual satisfaction with decision than O'Connor's decisional conflict scale and is comparable to the Sainfort Post Decision Satisfaction Scale. Since pilot work showed that 48% of 73 transplant patients indicated the highest level of satisfaction with their treatment decisions on the Holmes-Rovner satisfaction scale, results will be dichotomized into maximally satisfied vs. less than maximally satisfied. Regret will be measured at 3 months with two items (wish to change one's mind, and feeling that one would be better off another treatment had been selected) measured on a 6-point Likert scale reflecting frequency of feelings. Cronbach's alpha was 0.80 in a study of 201 men with prostate cancer.

These variables will be assessed at:

- 1) Study enrollment.
- 2) After approximately 1 month from study enrollment and at least 28 days from last therapy cycle.
- 3) After approximately 3 months from study enrollment and at least 28 days from last therapy cycle.
- 4) After approximately 6 months from study enrollment and, if necessary, adjusted within a limit of 30 days to have this assessment done prior to treatment with either allogeneic HCT or additional non-transplant therapies.
- 5) At 3, 6, 12, and 18 months after day 0 of allogeneic HCT for recipients of HTC or at 9, 12, 18, and 24 months from study enrollment for patient not treated with HCT.

8.1.17 **Frailty**

Frailty will be evaluated according to the five criteria proposed by Fried,[67] following the original cut-off points, with some modifications[102]: 1) Unintentional weight loss (Shrinking) of $\geq 5\%$ in the last year. 2) Low energy (Exhaustion): Based on two questions asking about interest or pleasure in doing things and asking about feeling down, depressed or hopeless. Those who answered "more than half of the days" or "nearly every day" to at least one of these questions were considered to meet this

Protocol 2368.00

criterion. 3) Weakness: The Timed Up and Go is a performance test of physical mobility. The test measures how many seconds it takes an individual to stand up from a standard armchair (approximate seat height of 46 cm), walk a distance of 3 m (10 ft), turn, walk back to the chair, and sit down again. The test was originally reported by Mattias et al., and subsequently modified by Podsiadlo et al.[103] to be a timed test. In a population of frail, community-dwelling older adults, there was good interrater and intrarater reliability (intraclass correlation coefficient = 0.99 for both). The Timed Up and Go score correlated to the scores on the Berg Balance Scale (correlation coefficient [r] = -0.72), gait speed (r = -0.55), and Barthel Index of ADL (r = -0.51) [103]. Guralnik et al.[71] reported gait speed as an important predictor of disability. Duration <7 seconds will meet criteria of frail for weakness. 4) Slowness: Calculated after walking 4 meters, adjusted for sex and height, according to Fried. The cut-off points for 4 meters were established as, in men: height \leq 173 cm and time 0.65 m/s; height >1.73 cm and time 0.76 m/s; and for women: height \leq 1.59 cm and time 0.65 m/s; and height >1.59 cm and time 0.76 m/s. 5) Low physical activity: will be captured by the MOS Physical Health Scale. Patients scoring in the lowest 20% will be assigned a point for frail for physical activity.

Based on the above five criteria, which incorporates two performance-based measures (timed up-and-go and walk speed over 4 meters) and three self-report measures (exhaustion, weight loss, and physically frail), range of scores will be 0-5; 1-2 indicates pre-frail, 3-5 indicates frail.

FI score will be assessed at:

- 1) Study enrollment.
- 2) After approximately 6 months from study enrollment and, if necessary, adjusted within a limit of 30 days to have this assessment done prior to treatment with either allogeneic HCT or additional non-transplant therapies.
- 3) At 18 months after day 0 of allogeneic HCT for recipients of HTC or 24 months from study enrollment for patient not treated with HCT.
- 4) If no clinical appointments, the timing can be expanded to within 6 months of the above time points.

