In order to address these limitations, the CCI was modified in a way that better detected comorbidities among HCT recipients [74]. First, the definitions of several comorbidities were modified by adding progressive impairments of diffusion capacity of carbon monoxide (DLCO) and/or forced expiratory volume in 1-second (FEV1), left ventricular ejection fraction (LVEF) of $\leq 50\%$, and progressive elevations of levels of bilirubin and hepatic transaminases to the clinical definitions of pulmonary, cardiac, and hepatic comorbidities, respectively. In addition, new cut-offs for serum creatinine levels were set to better define renal comorbidity. Second, all comorbidities encountered in transplanted patients were included in the risk assessment analysis.

Protocol 2368.00

The study included 1055 patients with different hematological diseases who were given allogeneic HCT after nonmyeloablative (n=249) or myeloablative (n=761) conditioning. Two thirds of the patients were randomly assigned to a training set and one third to a validation set. Integer weights of comorbidities were calculated based on adjusted HRs from Cox proportional hazard models of 2-year NRM. The new HCT-CI included 17 comorbidities acquiring scores from 1 to 3.

In the training set, HCT-CI scores of 0, 1, 2, 3, ≥ 4 predicted 2-year NRM of 9%, 14%, 27%, 41%, and 43%, respectively. In the validation set, HCT-CI scores showed higher sensitivity than the CCI scores in capturing comorbidities. HCT-CI scores of 1-2 and ≥ 3 were found in 34% and 28% of patients, while only 10% and 3% of patients had CCI scores of 1 and ≥ 2 , respectively. The HCT-CI scores of 0, 1-2, and ≥ 3 showed good discrimination of NRM (14%, 21%, and 41%) and survival (71%, 60%, and 34%), respectively (**Figure 2**).

The discriminatory capacity of the HCI-CI and CCI, defined as the ability of the model to separate those patients who survived from those who died, were compared using the *c*-statistic or concordance index [75], which was identical to the area under a receiver operating characteristic curve (AUC). A *c*-statistic value of 1.0 indicated perfect predictive discrimination and a value of 0.5 indicated no ability to discriminate. The HCT-CI scores showed higher discriminative power than the CCI scores both for NRM (*c*-statistic of 0.692 versus 0.546, $P < 0.001$) and survival (*c*-statistic of 0.661 versus 0.561, $P < 0.001$).

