8.1.3 PFT, Blood Tests, and Urine Analysis (for patients of FHCRC only)

8.1.3.1 Pulmonary function tests: particularly, diffusion capacity of carbon monoxide (DLco) after correction for hemoglobin and forced expiratory volume in one second (FEV1).

8.1.3.2 Serum ferritin, albumin, C-reactive protein (CRP), and vitamin D.

8.1.3.3 Urine test: Albumin-creatinine ratio, as well as urine analysis.

These variables will be assessed once at:

- 1) Study enrollment.

8.1.4 HCT-CI, comorbidities, and laboratory tests:

8.1.4.1 Left ventricular ejection fraction, if available or clinically indicated. The closest value (include the date) to the study assessment point. Liver function tests: particularly, total and direct bilirubin, aspartate aminotransferase, alanine aminotransferase, and albumin. The closest values (include the dates) to the study assessment point.

8.1.4.2 Weight and height and calculation of body mass index. The closest measurements (include the dates) to the study assessment point

8.1.4.3 Laboratory tests, if available or clinically indicated: The closest values (include the dates) to the study assessment point:

8.1.4.3.1 Absolute neutrophil count.

8.1.4.3.2 Hematocrit percentage.

8.1.4.3.3 Platelet count.

8.1.4.3.4 Serum creatinine.

8.1.4.3.5 Lactate dehydrogenase.

8.1.4.3.6 Serum ferritin.

8.1.4.3.7 Beta-2 microglobulin.

8.1.4.4 HCT-CI total score and positive comorbidity findings (Please see study documents for HCT-CI and the comorbidity coding tool). If some of the comorbidities included in the HCT-CI were not assessed for a patient, then indicate not available or "NA".

8.1.4.5 Other positive comorbidities, which are not included in the HCT-CI.

These variables will be assessed at:

- 1) Study enrollment.
- 2) After approximately 3 months from study enrollment and at least 28 days from last therapy cycle.
- 3) After approximately 6 months from study enrollment and, if necessary, adjusted within a limit of 30 days to have this assessment done prior to treatment with either allogeneic HCT or additional non-transplant therapies.

8.1.5 Karnofsky performance status (KPS) percentage:

Protocol 2368.00

Please see study document 'The Karnofsky Performance Status Scale' for KPS assessment.

- 8.1.5.1 As prospectively assessed and documented by clinicians.
- 8.1.5.2 If not assessed by clinicians at the required study time points: there two options.
- 8.1.5.3 Request KPS assessment from treating physician.

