8.1.19 Questions about some geriatric problems only for patients 60 years and older

The questionnaire will ask the following questions:

- 8.1.19.1 Vision
- 8.1.19.2 Hearing
- 8.1.19.3 Other physical problems or illness
- 8.1.19.4 Falls

These variables will be assessed once at:

- 1) Study enrollment

8.1.20 Recovery Survey:

The recovery survey will ask the following questions:

- 8.1.20.1 Marital status
 - 8.1.20.1.1 Change since diagnosis of AML
 - 8.1.20.1.2 Current marital status.
- 8.1.20.2 Work status
 - 8.1.20.2.1 Change since diagnosis of AML
 - 8.1.20.2.2 Current work status.
- 8.1.20.3 Family income
 - 8.1.20.3.1 Change since diagnosis of AML
 - 8.1.20.3.2 Current income.

These variables will be assessed once at:

- 1) 24 months from study enrollment.

Protocol 2368.00

Table 1: Timing of Study Evaluations*

	Timing of assessments							
		Months						
Measures	Enrollment	1	3	6 ∇	9 ∇	12 ∇	18 ∇	24 ∇
	£							
Patient-reported socio-demographic & health behaviors survey	X							
AML diagnostic features	X							
HCT-CI, comorbidities, and laboratory tests	X		X	X				X
KPS	X		X	X	X	X	X	X
Physician preference surveys	X	X	X	X**				
Patient Preference Survey	X	X	X	X**				
Availability of donor, and its type	X	X		X				
Treatment details		X	X	X	X	X	X	X
AML response evaluations		X	X	X	X	X	X	X
Toxicity grading		X	X	X	X			X

Protocol 2368.00

QOL measures in Questionnaire Packet	X	X	X	X	X	X	X	X
Function measures (Walk Test)	X	X	X	X	X	X	X	X
Timed Up-Go test for FI calculation	X			X				X
Cognition in older patients	X					X		X
Geriatric problems in older patients	X							
Outcomes data		X	X	X	X	X	X	X
PFT, Blood Tests, Urine test (FH site only)	X							
Patient-reported Recovery survey								X

*All dates of assessments are recommended dates that could be adjusted (within a limit of 30 days) to take into account suitability of patients' clinical status and reasonable recovery of peripheral blood counts.

[figure not shown]
[figure not shown]
**Assessment will be done if the patient has not undergone HCT

£Assessment should be done after enrollment and preferably before the start of treatment. However, a grace period of one week after the start of treatment is allowed to consent the patient and introduce the assessments. Surveys should be completed by the patients based on their experiences before start of treatment and they should be returned as soon as possible after being completed.

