11.0 STATISTICAL CONSIDERATIONS

11.1 Introduction and sample size

To improve the strength of the findings as well as reporting of these findings, we will follow the recommendations of STROBE Statement (see study document ‘STROBE Criteria’) which provides guidelines of how to discuss and report study design, analysis, and findings in manuscript writing.

There is no targeted number for enrollment on this study. Instead, we plan to enroll all eligible patients continuously for duration of 36-40 months from study activation. We anticipate enrolling approximately 1000 patients from all sites but we will allow enrollment of more patients if enrollment rates were unexpectedly higher.

Based on a preliminary screen of the SCCA records over years 2008-2009, approximately 180, 125, 120, and 75 eligible patients with AML were seen annually at the 4 collaborating institutions, respectively, for an annual total of 500 patients. We anticipate enrollment rate of approximately ~65% resulting in a total of approximately 1000 patients observed over 3 years. Based on a preliminary screen, we anticipate that 50% (n=500) will be ≥60 years of age. Among the remaining 500 younger patients, we would anticipate (based on historical distribution of comorbidity scores among HCT recipients) that approximately 35% (n = 170) will have significant comorbidities (scores of ≥3). This suggests that the combined cohort of older or medically infirm patients eligible for studying the rate of receiving allogeneic HCT will be approximately 670 patients over 3 years. **Table 2** shows an estimate of the minimal increment in incidence of HCT detectable with 80% power at the 2-sided 0.05 level of significance, for varying assumptions about the prevalence of the risk factor. These estimates assume a time-to-event analysis, 25% overall incidence at 2 years post-initial therapy and 25% incidence of death without HCT as a competing risk.

Prevalence of risk factor or group	Increment in HCT incidence (HR)
10%	0.17 (1.9)
20%	0.13 (1.7)
30%	0.11 (1.6)
40%	0.10 (1.6)

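### For patients enrolled in the one-week grace period, the closest-value rule can put on-treatment results into the enrollment HCT-CI

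*Combined protocol and SAP*

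**What the plan says.** **Which value is recorded.** Section 8.1.4 takes liver tests and the listed laboratory tests, including creatinine, as "The closest values (include the dates) to the study assessment point". LVEF follows the same rule. The rule is two-sided: it does not ask that the enrollment value come before treatment.

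**How the score is made.** Item 8.1.4.4 asks for "HCT-CI total score and positive comorbidity findings (Please see study documents for HCT-CI and the comorbidity coding tool"). Those study documents are separate and were not available for this review. Section 3.7 says that the index's hepatic item uses "progressive elevations of levels of bilirubin and hepatic transaminases", that its cardiac item includes an LVEF cut-off, and that its renal item uses creatinine cut-offs.

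**When enrollment assessment happens.** The enrollment footnote to Table 1 says "Assessment should be done after enrollment and preferably before the start of treatment", and then that "a grace period of one week after the start of treatment is allowed to consent the patient and introduce the assessments". It continues: "Surveys should be completed by the patients based on their experiences before start of treatment". It gives no matching instruction for laboratory values or the HCT-CI.

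**What the score is used for.** Section 11.1 forecasts that, of 500 patients under 60, "approximately 35% (n = 170) will have significant comorbidities (scores of ≥3"), giving a combined older or medically infirm cohort of about 670. Section 11.2 compares that cohort with all other patients on the rate of HCT. Section 11.3 compares outcomes within it and lists comorbidities among the adjusters.

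**The concern.** A baseline comorbidity score should describe the patient before the treatment under study. If a patient is consented on day 5 of induction, the value closest to the assessment is the day-5 value. Bilirubin, transaminases and creatinine can all change in the first week of chemotherapy. The enrollment score would then mix prior comorbidity with early treatment effect.

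Two uses are exposed. The first is objective 5.1.1.1, where a shift across the threshold moves a patient under 60 from the comparator to the infirm group. The second is objective 5.1.2, where the score is a covariate for patients of every age. Early toxicity can plausibly lower the chance of HCT and raise the risk of death, so the link between infirmity and these outcomes could be overstated.

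There is also a risk of double counting. Grade III-IV toxicity is collected from about month 1 (Section 8.1.11) and compared between treatments (Section 11.3), so one first-week laboratory change could be recorded both as baseline comorbidity and as toxicity.

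Only patients who use the grace period are affected, and their share may differ between sites.

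**Working it through.** **1. Reproduce the plan's counts.** The inputs are in Section 11.1: 500 patients aged 60 or over, 500 younger, and 35% of the younger with scores of 3 or more.
- 0.35 × 500 = 175 (stated 170)
- 500 + 175 = 675 (stated 670)

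Both agree to within 3%. Section 11.2 gives 40% for the same 170. Since 0.40 × 500 = 200, the 35% is the figure that fits. I use the stated counts below. Younger patients with scores under 3 number 500 − 170 = 330.

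**2. Compare the timing rules.**

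| Item | Protection against treatment effects |
|---|---|
| Surveys at enrollment (Table 1 footnote) | Answered from pre-treatment experience |
| Research blood sample, Seattle site (Sections 9.0 and 10.0) | Drawn before therapy |
| HCT-CI at month 3 (8.1.4) | At least 28 days after the last cycle |
| HCT-CI at month 6 (8.1.4) | May be shifted to precede HCT or further therapy |
| HCT-CI at enrollment (8.1.4) | None stated |

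Of the three time points listed in 8.1.4, the enrollment score is the one without an anchor, and it is the natural candidate for classifying patients.

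**3. Who can change group.** Patients aged 60 or over are in the cohort by age, whatever their score. An upward error can reclassify only the 330.

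**4. Illustrative size.** The documents give neither the share assessed after treatment start nor the rate of score change. All three shares here are assumptions: 20-40% assessed late, 10-20% of those gain at least one point, and one third to one half of those reach 3 or more.
- Low: 330 × 0.20 × 0.10 × 1/3 = 2.2
- High: 330 × 0.40 × 0.20 × 1/2 = 13.2
- Against 170: 2.2/170 = 1.3%; 13.2/170 = 7.8%
- Against 670, using 2 and 13 patients: 2/670 = 0.3%; 13/670 = 1.9%

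A wider assumption (10-50% assessed late, 5-20% of those crossing the threshold) gives 330 × 0.10 × 0.05 = 1.7 to 330 × 0.50 × 0.20 = 33 patients. The upper end would be 33/(170 + 33) = 16% of the enlarged younger infirm group and 33/(670 + 33) = 4.7% of the enlarged cohort.

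**5. Effect on the primary contrast, unfavourable case.** Assume 25% HCT in both groups (the overall figure in Section 11.1), so 0.25 × 670 = 167.5 and 0.25 × 330 = 82.5 transplants. Move 13 patients into the infirm group and let none of them reach HCT.
- Infirm: 167.5/683 = 24.5%
- Others: 82.5/317 = 26.0%
- Spurious gap: about 1.5 percentage points

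The smaller group is about a third of patients. At 30-40% prevalence, Table 2 gives detectable increments of 10-11 points.

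**The case against.** The strongest reply has five parts.

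- **The scoring link is not documented.** Items 8.1.4.1 to 8.1.4.3 say what to record. The score is a separate item governed by a coding tool that may contain its own timing rule. This stands. A reader might infer that a day-5 value necessarily enters the score, but the documents show only that the protocol text allows it.
- **The grouping rule is implied.** The threshold of 3 appears in a sample-size forecast, and Section 11.2 speaks only of high scores. A reader might infer that the protocol defines medically infirm by the enrollment score. It does not say so. This also stands.
- **Late assessment is meant to be the exception.** Assessment before treatment is preferred, and Section 7.0 has patients approached at the initial consultation. This limits the size but does not remove the gap.
- **The size is small and assumed.** On the base that the primary contrast uses, 0.3-1.9% of 670 is minor, and the wider range shows that the figure cannot be pinned down. Section 11.3 also adjusts for institution, which deals with part of any site difference in the outcome comparison.
- **Dates are already recorded.** Post-start values can therefore be identified later. That makes correction easy, but nothing in the plan says that it will be done.

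Two other inferences go too far. One is that counts, LDH and weight distort the score: Section 3.7 does not tie them to it. The other is that the infirm group must look worse than it is: some values may improve after treatment starts, so the direction is not certain.

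**Conclusion.** The gap is real and narrow. Followed as written, 8.1.4 together with the Table 1 footnote can put on-treatment liver tests, creatinine or LVEF into a score meant to describe the patient at baseline. This holds unless the unseen coding tool prevents it, and the effect on grouping depends on the enrollment score being what defines the medically infirm group.

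The documents do not support a claim that the primary contrast is materially biased, or biased in a known direction. Under the narrower assumptions about 2 to 13 younger patients change group, and even an unfavourable case with 13 produces a spurious gap of about 1.5 points. The effect on the score as an adjuster reaches late-assessed patients of all ages and cannot be sized from the documents.

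The change is worth making because it is cheap and protects a variable that feeds both primary objectives.

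**What to change.** In 8.1.4, for the enrollment time point only:

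1. Take the last laboratory or LVEF value on or before the first day of the current treatment course, and score the enrollment HCT-CI from it. For patients entering with refractory or relapsed disease, this means the current salvage course.
2. Still count comorbidities that existed before treatment but were first documented after it started. Scoring only from findings dated before treatment would drop long-standing conditions first written down in the first week. The item would become NA, and the protocol text does not say how NA is scored.
3. Where only a post-start value exists, use it, flag it, and repeat the analyses without those patients.
4. Keep the closest-value rule at 3 and 6 months.
5. Check that the coding tool agrees. State in Section 11 that the enrollment score defines the medically infirm group, if that is the intention.

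The cost is a sentence or two in 8.1.4, the matching form guidance and one sensitivity analysis. Value dates are already collected, so enrolled patients can be re-scored from charts without new visits. The downside is slightly older values for some patients and a small number of flagged items.
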